Participants who take psychotropic medications will be asked to remain consistent on the seven days of the trial (i.e., choose to take or not take medications each day that the VR headset is used). The general course of such medication involves such decisions daily, so participants will have received medical consultation from their prescribing physician outside of the context of the study. Participants who have questions about stopping medication will not be advised by the study staff. They will be encouraged to discuss with their prescribing physician. While participating in the VR intervention, they will be wearing a VR headset while completing homework and studying on a laptop. 40 minutes of each session are devoted to work completion. Participants may be offered to complete all 40 minutes at once or to take a 10-minute break. If a session does not meet a 45-minute threshold, the participant will be scheduled to repeat the session.

Initial evaluation: Participants in each phase will complete an initial diagnostic evaluation to confirm eligibility and collect baseline data. The first half of the evaluation will be done via electronic surveys hosted by Rutgers. Subjects will provide contact, demographic, and background information. To measure current symptoms of ADHD and inform diagnosis, they will complete the Barkley Adult ADHD Rating Scale (BAARS-Self). To capture potential risk factors for use of the VR system, prescreening questions will ask about related medical history. To evaluate other services and treatments participants may be receiving, they will complete the Service Utilization for College Student's Questionnaire. To obtain a baseline of treatment targets/mechanisms, participants will complete the Adult Concentration Index, Homework Motivation, and Homework Effort/Efficiency ratings. To measure potential treatment moderators and outcomes, subjects will complete the GAD-7 and PHQ-9, Columbia Suicide Severity Index (CSSI), BDEFS, BFIS, and surveys on Academic Record (self-report only; and GPA & Percentage

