VR intervention: After completing the initial evaluation and confirming eligibility, a new sample of 45 participants will be randomized to 1 of 3 groups and then scheduled to use the VR headset in their room/home or the library. Randomization will be performed (1:1:1) to the three conditions. Randomization will be blocked on ADHD medication status to ensure an equal number of participants taking and not taking ADHD medication in each group. Phase 3 includes a 2-session baseline where all participants complete homework and study outside of VR (total of 12 sessions; 2 non-VR baseline and 10 in VR condition). During each session, participants will complete a set of standardized reading comprehension problems to determine how many they complete and how accurately. LSU and Rutgers study staff will run VR intervention visits at their respective study sites.

Group 1, VR passthrough: After completing the two session non-VR baseline, participants will use the VR headset in their room/home or the library 10 times over three weeks (max twice a day with a minimum 2-hour break) for 1-hour sessions each time. The participant will wear the headset, but it will not be used as usual. The headset will be in “VR passthrough” mode, meaning the participant will see through to the normal environment and laptop (i.e., they can see the real world around them, just wearing a headset).

Group 2, VR environment only: After completing the two session non-VR baseline, participants will use the VR headset in their room/home or the library 10 times over three weeks (max twice a day with a minimum 2-hour break) for 1-hour sessions each time. The participant will wear the VR headset and engage in homework in the VR environment.

Group 2, VR environment + contingency management: After completing the two session non-VR baseline, participants will use the VR headset in their room/home or the 10 times

over three weeks (max twice a day with a minimum 2-hour break) for 1-hour sessions each time. The participant will wear the VR headset and engage in homework in the VR environment while receiving contingency management (real-time feedback on performance through red or green light FlowLight icon).

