In-Session Assessment: As with Phases 1 and 2, participants will first complete 10 minutes of standardized reading comprehension passages and questions before being automatically prompted on their VR screen to complete 40 minutes of studying in either pass-through, VR immersive mode, or VR immersive mode with contingency management. After the allotted 40 minutes, participants will then be asked to complete 10 minutes of brief rating scales asking about feasibility/usability of using VR to complete work, attention/concentration, and homework effort. Specifically, participants will complete the Adult Concentration Inventory, the Homework Motivation Index, and the Homework Effort Index each session. Finally, they will answer a question about whether or not they took ADHD medication that day – the Current Day Medication Adherence. Participants will complete the 10-item Systems Usability Scale after sessions 4 and 12 only.

Outcome Assessment: Following the 12th session, participants will complete an outcome assessment. For the outcome assessment, they will complete some of the same outcome battery described in Phase 1 and 2 (BAARS-Self, BDEFS, BFIS, Academic Records, GPA & Percentage of Assignments Completed). Questions on feasibility and usability of the VR system will be asked in the outcome assessment. Outcome assessments will be performed by Rutgers study staff using Rutgers-hosted REDCap.

Follow-Up Assessment: Three months after the completion of the final session, participants will complete a follow-up assessment visit. The assessment battery will be the same as the outcome battery described in the initial outcome assessment. Follow-up assessments will be performed by Rutgers study staff using Rutgers-hosted REDCap.

PHASE 4: Conduct a larger parallel group randomized trial.

Phase 4 will follow the same procedures as Phase 3 (see above) except instead of n=45, we will randomize n=252 (note, number who consent is higher, to account for those found not eligible after consenting). This will be done across several cohorts. Please see the study timeline figure in section 1.10 for a visual of how many subjects will be in each cohort.

B. Data Points

PHASE 1: Refine objective data capture techniques.

Initial evaluation:

- Contact, demographic, and background information
- Service Utilization for College Students
- Current Day Medication Adherence survey
- BAARS-Self
- Pre-screening questions
- Adult Concentration Index (ACI)
- RCADS

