- Service Utilization for College Students
- Current Day Medication Adherence survey
- BAARS-Self
- Pre-screening questions
- Adult Concentration Index (ACI)
- GAD-7
- PHQ-9
- Columbia Suicide Severity Index
- WHODAS (Required by NIMH/NDA)
- DSM-5 Level 1 Cross-Cutting Symptom Measure (Required by NIMH/NDA)
- BDEFS – Short Form
- BFIS
- Baseline Homework Motivation Index
- Baseline Homework Effort Index
- Academic Record (GPA & Percentage of Assignments Completed)
- Reading Comprehension Standardized Assessment
- SCID-V RV

Each of 10 sessions:

- Key strokes and mouse clicks
- Reading Comprehension Standardized Assessment
- Periodic screenshots of participant screens
- 10-item Systems Usability Scale (Sessions 4 and 10 only)
- Adult Concentration Inventory
- Homework Motivation Index
- Homework Effort Index
- Current Day Medication Adherence

Outcome Assessments:

- Current Day Medication Adherence survey
- BAARS-Self
- BDEFS – Short Form
- BFIS
- Academic Record (GPA & Percentage of Assignments Completed)
- Feasibility and usability of the VR systems

3-Month Follow-Up

- Current Day Medication Adherence survey
- BAARS-Self
- BDEFS – Short Form
- BFIS
- Academic Record (GPA & Percentage of Assignments Completed)
- Feasibility and usability of the VR systems

C. Study Duration

PHASE 1:

Each participant will be involved for approximately 4 weeks (1 week of initial evaluation, 2 weeks of intervention, 1 week of outcome assessment).

The initial evaluation will take approximately 1.5 hours.

Each VR intervention session will take approximately 1 hour (10 minutes of reading comprehension questions, 40 minutes of intervention, 10 minutes to complete surveys). Across the intervention, they will complete 10 1-hour sessions.

The outcome assessment will take approximately 30 minutes to complete, and the follow-up phone interview with the research team should take 15 minutes.

PHASE 2:

Each participant will be involved for approximately 5 weeks (1 week of initial evaluation, 2 weeks of intervention, 1 week of outcome assessment, 1 week of focus group).

The initial evaluation will take approximately 1.5 hours.

Each VR intervention session will take approximately 1 hour (10 minutes of reading comprehension questions, 40 minutes of intervention, 10 minutes to complete surveys). Across the intervention, they will complete 10 1-hour sessions.

The outcome assessment will take approximately 30 minutes to complete.

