Within 6 months of the conclusion of the participation in the intervention, participants will participate in a focus group. The focus group will take approximately 90 minutes.

PHASE 3:

Each participant will be involved for approximately 18 weeks (1 week of initial evaluation, 1 week of intervention baseline, 3 weeks of intervention, 1 week of outcome assessment, then a 3-month follow-up).

The initial evaluation will take approximately 1.5 hours.

Each VR intervention session will take approximately 1 hour (10 minutes of reading comprehension questions, 40 minutes of intervention, 10 minutes to complete surveys). Across the intervention, they will complete 12 1-hour sessions (2 baseline without VR headsets, 10 in the assigned condition).

The outcome assessments will take approximately 30 minutes.

The 3-month follow-up will take approximately 20 minutes to complete.

PHASE 4:

Each participant will be involved for approximately 18 weeks (1 week of initial evaluation, 1 week of intervention baseline, 2 weeks of intervention, 1 week of outcome assessment, then a 3-month follow-up).

The initial evaluation will take approximately 1.5 hours.

Each VR intervention session will take approximately 1 hour (10 minutes of reading comprehension questions, 40 minutes of intervention, 10 minutes to complete surveys). Across the intervention, they will complete 12 1-hour sessions (2 baseline without VR headsets, and 10 in the assigned condition).

The outcome assessments will take approximately 30 minutes.

The 3-month follow-up will take approximately 20 minutes to complete.

D. Endpoints

Participants will be removed from the study if they have an adverse reaction to the VR headset, such as nausea or dizziness, that taking breaks and making adjustments to the VR headset is not able to address.

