4.6 Economic Burden and/or Compensation for Subjects

A. Expenses

Subjects will not be charged for their participation in this study, including the assessment and treatment sessions.

B. Compensation/Incentives

PHASE 1.

- Subjects will be paid \$40 for completion of all the baseline inclusion/exclusion measures and the SCID interview.
- Participants will be paid \$110 for completion of the intervention and all of the post-intervention measures. This is appropriate given that participants are devoting 1 hour of time 10 times over two weeks (max twice a day with a minimum 2-hour break) and 45 minutes for the outcomes questionnaires and follow-up phone interview.

PHASE 2.

- Subjects will be paid \$40 for completion of all the baseline inclusion/exclusion measures and the SCID interview.
- Participants will be paid \$110 for completion of the intervention and all of the post-intervention measures. This is appropriate given that participants are devoting 1 hour of time 10 times over two weeks (max twice a day with a minimum 2-hour break).. They will receive an additional \$25 gift card for participation in the focus group.

PHASE 3 and PHASE 4.

- Subjects will be paid \$40 for completion of all the baseline inclusion/exclusion measures and the SCID interview.
- Participants will be paid \$110 for completion of the intervention and all of the post-intervention measures in two parts: \$60 after completing 7 sessions within 2 weeks, and an additional \$50 after they complete all 12 sessions within 3 weeks. Payment will happen at the end of the study participation period of 3 weeks as a single e-gift card. This is appropriate given that participants are devoting 1 hour of time 12 times over three weeks (max twice a day with a minimum 2-hour break).
- Participants in the VR + feedback group will be paid up to \$130 if they maintain at least a 25% increase in focus over their baseline sessions 1 & 2 for a \$10 bonus. They can receive this bonus at the end of 7 sessions based on performance up to that point, and then again at the end of 12 sessions for a total reward compensation of \$20.
- They will receive an additional \$25 gift card for completion of follow-up measures 3 months post the final treatment session.

C. Compensation Documentation

E-gift cards will be sent electronically (i.e., a code will be emailed to participants, no emails will be given directly to the company [e.g. Amazon]). A record of codes sent to subjects will be kept.

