analyzed using MPlus will address missing data using full information maximum likelihood estimates. This approach makes full use of available data and is one of several procedures considered the state of the art for addressing missing data.

Intent to Treat Analysis: An intent-to-treat approach will be used to analyze the data, wherein each participant will be kept in the group to which they were randomized for analysis, regardless of treatment compliance. A mixed-effects model will be used to account for the repeated-measure nature of the study design. Time will be treated as a dummy-coded categorical variable using baseline as the reference. A student-level random effect will be included and modeled using an auto-regressive covariance structure to account for within-subject dependence due to repeated measurements. The models will also include treatment condition as a student-level fixed effect, and condition x time interaction effects. This modeling will allow us to compare baseline to 8-week (post) changes, and the extent to which these changes differ across conditions.

Mediator Analyses: Mediational analyses will be conducted using structural equation modeling. There are advantages of a structural equation modeling approach to estimating and determining the significance of indirect effects within mediational models and outlined specific estimation procedures that are available in MPlus. All analyses will be conducted in MPlus which provides estimates that partition the total effect of an independent variable on a dependent variable into the direct and indirect effects using bootstrap estimation procedures. Preliminary analyses will be conducted separately for each mediator. Scores on the mediator will be modeled as a function of pretest scores on the mediator, intervention condition, and covariates. The intervention's effect can then be partitioned into the direct effect on changes (e.g., on school grades) at posttest and follow-ups and the indirect effects via the mediator. These initial analyses will be used to guide a more comprehensive model that will incorporate mediators that emerge as significant within the individual models. Primary mediation analyses will focus on whether change in the proposed mechanisms of action mediates improvement in AIM total scores and BDEFS.

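### For concentration, motivation and effort the Phase 4 model does not say which of two baselines is its reference, and it takes change from baseline instead of adjusting for the pre-randomization rating; the cost is precision, not bias in the randomized contrast

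*Combined protocol and SAP*

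**What the plan says.** Section 1.3 A, under Initial evaluation, names the baseline for the three self-ratings: "To obtain a baseline of treatment targets/mechanisms, participants will complete the Adult Concentration Index, Homework Motivation, and Homework Effort/Efficiency ratings". The Phase 3 and 4 list in section 1.3 B agrees. At that visit it places the ACI, the "Baseline Homework Motivation Index" and a matching effort index.

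Section 1.3 A, Phase 3, sets up a second baseline: "Phase 3 includes a 2-session baseline where all participants complete homework and study outside of VR". Phase 4 takes it over by cross-reference ("Phase 4 will follow the same procedures as Phase 3 (see above"), and section 1.3 C counts "12 1-hour sessions (2 baseline without VR headsets, and 10 in the assigned condition". The Phase 3 in-session assessment says that "participants will complete the Adult Concentration Inventory, the Homework Motivation Index, and the Homework Effort Index each session", with no exception for the first two. Section 4.6 B also uses sessions 1 and 2 as a baseline, but for focus and for a payment: the VR + feedback arm earns a bonus if participants "maintain at least a 25% increase in focus over their baseline sessions 1 & 2".

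The intent-to-treat paragraph of section 6.1 then says: "Time will be treated as a dummy-coded categorical variable using baseline as the reference". The model has condition, time and their interaction. It does not say which assessment is the reference, or whether two sessions would be averaged or kept as separate time levels. It does not list the baseline value of the outcome as a covariate.

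**The concern.** An analyst could follow either passage and report a different contrast for concentration, motivation and effort, which are three of the four dependent variables in section 1.6 B. The fourth, on-task behavior, has no measure listed at the initial evaluation, so its reference would have to be a session in any case.

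The two candidates differ in kind. One is a single rating before randomization with no work session attached. The other is a pair of ratings after work blocks. If the initial evaluation is the reference, sessions 1 and 2 become time points after baseline at which no arm has yet had its intervention.

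Two things are at stake. The first is the precision of the randomized contrast. The second is the meaning of within-arm change. Section 6.1 makes effect sizes for time a Phase 3 result, and with the online survey as reference these would include the shift from survey to post-work rating. For concentration they would also include regression to the mean, because section 4.1 C uses the ACI as an entry criterion.

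**Working it through.** **The plan's own figure.** Section 1.5 gives 84 per arm (252 / 3), with d = 0.4 for VR only against each other arm. It states no alpha, power, dropout or repeated-measures correlation, so 84 can be neither confirmed nor refuted. At two-sided 5% without baseline information, 84 per arm gives 73.6% power at d = 0.4, and 80% would need 99 per arm. No standard error is stated anywhere.

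**Assumptions.** Unit SD at each occasion, 84 per arm, no dropout, and one post time point (session 12), because section 6.1 compares baseline with a single post value. Let r be the correlation between any two session ratings and r0 the correlation of the initial-evaluation rating with a session rating. SE = sqrt(2V/84), where V is the variance of the change score or the residual variance. Power = Φ(0.4/SE − 1.96).

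**Step 1: change from each candidate.**
- Initial evaluation: V = 1 + 1 − 2·r0 = 2(1 − r0).
- Mean of sessions 1 and 2: V = 1 + (1 + r)/2 − 2r = 1.5(1 − r).
- With r0 = r, the SE ratio is sqrt(2/1.5) = 1.155 at any r.
- Under AR(1) over occasions 0 to 12, with or without a random intercept, the ratio runs from 1.04 to 1.155.
- With r = 0.5 and r0 = 0.5, 0.4 and 0.3, V is 1.0, 1.2 and 1.4 against 0.75. The ratios are 1.155, 1.265 and 1.366.
- With r = 0.6 and r0 = 0.3, the ratio is sqrt(1.4/0.6) = 1.53, so the upper end depends on the pair assumed.
- If the session reference were session 1 alone, the ratio under AR(1) would be 1.00 to 1.04.

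**Step 2: covariate instead of change.**
- Initial evaluation as covariate: V = 1 − r0². Relative to change from it, the SE is multiplied by sqrt((1 + r0)/2), which is 0.806 at r0 = 0.3 and 0.866 at r0 = 0.5.
- Both as covariates, r = 0.5: the two-session mean has variance 0.75 and covariance 0.5 with session 12, and covariance r0 with the initial rating. Explained variance is (0.25 − r0² + 0.75·r0²)/(0.75 − r0²). At r0 = 0.3 this is 0.2275/0.66 = 0.345, so V = 0.655. At r0 = 0.5 it is 0.1875/0.5 = 0.375, so V = 0.625.

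| Session 12, r = 0.5 | SE, r0 = 0.3 | SE, r0 = 0.5 | Power at 0.4 SD |
|---|---|---|---|
| Change from initial evaluation | 0.183 | 0.154 | 59%–74% |
| Initial evaluation as covariate | 0.147 | 0.134 | 78%–85% |
| Change from two-session mean | 0.134 | 0.134 | 85% |
| Both as covariates | 0.125 | 0.122 | 89%–91% |

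**Step 3: do sessions 1 and 2 carry the ratings?** For: section 1.3 A requires them at each session and numbers sessions to 12, and section 1.3 C counts 12 one-hour sessions, each with survey time. Against: the Phase 3 and 4 list in section 1.3 B gives them for 10 sessions, and the same list puts the later usability rating at session 10 where section 1.3 A puts it at session 12. The inference is reasonable but not settled by the text.

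**The case against.** The strongest reply is that the documents do name a baseline for these three ratings, and it is the initial evaluation. Section 1.3 C lists the initial evaluation and the intervention baseline as separate weeks, and section 4.6 B concerns focus, not self-ratings. The Phase 3 and 4 outcome list in section 1.3 B omits all three ratings, so the baseline-to-post contrast fits the functioning scales better, and those have one baseline. This has weight: no passage states that sessions 1 and 2 are the baseline for the ratings. It does not close the gap, because the ratings are declared dependent variables, section 6.1 gives no other Phase 4 treatment-effect model for them, and sessions 1 and 2 still have no stated role in it.

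A reader might infer that the standard errors differ by a third or more. For the planned single post time point that needs a clearly lower correlation for the online rating. Otherwise it needs a post value averaged over the 10 in-condition sessions (ratio 1.35 at equal correlations), a contrast the plan does not state.

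A reader might also infer that the survey-to-session shift biases the treatment comparison. It does not: the shift is common to all arms and cancels in expectation in condition by time.

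Finally, a reader might want sessions 1 and 2 made the primary reference because that is more precise. Section 1.3 A describes participants as randomized and then scheduled, so these sessions appear to follow allocation, and one arm is paid for improving on them. That makes them a doubtful primary reference.

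**Conclusion.** The concern holds as a gap in specification with a cost in precision. Two assessments are called baseline, and the model does not choose between them. Its change-from-baseline form uses the pre-randomization rating less efficiently than a covariate would. For one post time point, the initial-evaluation reference has a standard error 4% to 15.5% larger than a two-session mean under equal or AR(1) correlations, and about 37% larger at r0 = 0.3 with r = 0.5. Every correlation is an assumption, as are complete data and session 12 as the post value.

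The randomized contrast is unbiased in expectation with the initial evaluation as reference. It is also unbiased with sessions 1 and 2, provided that knowledge of allocation does not affect those ratings. Within-arm time effects are the exception: with the online survey as reference they mix in the change of setting and, for the ACI, regression to the mean. The documents do not allow that part to be sized.

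**What to change.** In section 6.1, for concentration, motivation and effort:

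1. Name the initial-evaluation rating as the pre-randomization baseline and enter it as a covariate, in place of relying on change from it.
2. State how sessions 1 and 2 enter, and that they are not post-intervention time points.
3. Use sessions 1 and 2 as an added covariate or as the reference only in a sensitivity analysis, unless allocation is concealed until after session 2. If it is, adjusting for both would bring the standard error to about 0.122–0.125 under the same assumptions.
4. Name the post value for these ratings.
5. State that Phase 3 effect sizes for time measured from the online survey include the change of setting.
6. Do the same for the mediator models, which already adjust for a pretest score but do not say which assessment it is.

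Reconcile the 10-session list in section 1.3 B with the 12 sessions in sections 1.3 A and 1.3 C. Limit any relabeling of the initial evaluation to Phases 3 and 4, since Phases 1 and 2 have no non-VR baseline sessions.

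The cost is wording. The initial-evaluation ratings are already planned, and if all 12 sessions carry the ratings no new data are needed.

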1.5 Sample Size Justification

PHASE 1: Refine objective data capture techniques. 30 participants completing 10 sessions will allow the team to implement and refine the keyboard and mouse click algorithms needed to ensure that we are tracking attention accurately. Since the goal is to refine the algorithms, no control group is needed.

PHASE 2: Develop and refine contingency management algorithms. 30 participants completing 10 sessions will allow for proper testing of the addition of the FlowLight icon (a stoplight) and box showing points earned within the VR environment. The goal is to understand how and when participants like to receive feedback about their on-task behavior and attention. A secondary goal is to understand how best to motivate participants to stay on-task and to complete work efficiently (e.g, a points system). 10 sessions with 30 participants are sufficient for this along with the focus group, and no control group is needed.

PHASE 3: Pilot test and evaluate impact on target mechanisms. 45 participants randomized to 1 of 3 groups will inform the feasibility and usability of the system tested and refined in phases 1 and 2. Though outcome measures will be collected, power analyses are not required due to the pilot status of the trial. The goal of phase 3 is to calculate effect sizes rather than to run statistical tests to begin to understand the magnitude of effects.

PHASE 4: Conduct a parallel group randomized trial. 252 participants randomized to 1 of 3 groups will allow for appropriate comparison across groups. Power calculations were run to determine this sample size. Power calculations are based upon $N = 84$ participants in each condition, for a total sample of 252 college students with ADHD. [name] prior intervention studies focused on improving attention produced effect sizes ranging from .6 to 1.12 comparing treatment to waitlist control. For the purposes of these power analyses, we use an effect size of .8 as the expected effect between the VR environment + contingency management group and passthrough control. This effect is also consistent with meta-analyses of behavioral contingency management interventions. Differences between active intervention conditions in our recent trial ranged between .4 to .6. Accordingly, between group effects (i.e., VR environment only to VR passthrough and to VR environment + contingency management) for the current study were estimated at $d = .4$.

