Phase 2: This project incorporates the contingency management procedures. Trends in motivation across sessions will be evaluated in relation to objective and rating scale metrics of attention and to FlowLight data. Focus groups will be audio-recorded and transcribed verbatim. The focus group data will be analyzed inductively for information relevant to feasibility and acceptability of the protocol. Two study personnel will separately code notes taken during the focus groups for emerging concepts and themes. Initial analysis will consist of identifying concepts found within the data through open coding. Inter-rater reliability checks will be used to compare the themes generated. Coding will continue until the point of saturation, that is, when no new concepts emerge. Data will be systematically analyzed according to the principles of thematic analysis, a method commonly used in qualitative research of this nature.

Phase 3. Because these analyses will focus on evaluating preliminary intervention effect sizes, outcome analyses will be conducted separately for each target mechanism. To compare groups, the variable (e.g., objective attention) will be entered analysis of variance (ANOVA), which will yield effect sizes for time and for interactions of time by intervention. The primary dependent variables will be objective assessment of attention and ratings of concentration, as well as ratings of homework effort and homework motivation. We will also compare trajectories of objective attention data across the three conditions.

Phase 4. The mixed model methodology planned and incorporated by the SAS GLIMMIX procedure can accommodate missing response data, thus allowing us to make use of all available data; note that covariate measurements are taken at baseline and should not be missing. Using Bayes' estimation, individuals with more data are given more weight in the calculation. This procedure is preferable in comparison to listwise or pairwise deletion in analyses where portions of the developmental curve are represented by differing individuals. In addition, we will check to see whether missing observations are missing at random, where we will test whether treatment group or any other covariate has an effect on the missing information. Any covariate associated with missing data will be included in the final model. Mediational models

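### As most naturally read, Phases 3 and 4 allocate before the two baseline sessions that set a cash target for one arm only, and nothing in the text withholds the arm until session 3

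*Combined protocol and SAP*

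**What the plan says.** **Order of events.** In section 1.3 A (Phase 3), once the initial evaluation has confirmed eligibility, "a new sample of 45 participants will be randomized to 1 of 3 groups and then scheduled to use the VR headset". The same paragraph adds that "Phase 3 includes a 2-session baseline where all participants complete homework and study outside of VR", and counts those two sessions within a total of 12. Each arm's description has its members finish the two sessions and then start with the headset. Section 1.3 C gives the sequence for Phases 3 and 4 as "1 week of initial evaluation, 1 week of intervention baseline", followed by the intervention. For Phase 4, section 1.3 A states: "Phase 4 will follow the same procedures as Phase 3 (see above", with 252 randomised in place of 45.

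**Bonus.** Section 4.6 B (Phases 3 and 4) pays $110 for the intervention and post-intervention measures. Only the VR + feedback group, which I take to be the VR + contingency management arm, can reach $130, "if they maintain at least a 25% increase in focus over their baseline sessions 1 & 2". The bonus is $10 after session 7 and $10 after session 12. Focus is not defined.

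**Measurement.** Section 1.3 B lists "Key strokes and mouse clicks" for Phases 3 and 4 under the 10 sessions, and lists no such measure at the initial evaluation. Section 1.6 B says on-task behaviour is measured inside the VR environment.

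**Analysis.** For Phase 3, section 6.1 says "The primary dependent variables will be objective assessment of attention and ratings of concentration", along with homework effort and motivation. It plans time and time-by-intervention effect sizes and a comparison of objective-attention trajectories across arms. Section 1.5 adds: "The goal of phase 3 is to calculate effect sizes rather than to run statistical tests". For Phase 4, section 6.1 gives a mixed model with baseline as the time reference, and mediator models that condition on the mediator's pretest.

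**The concern.** A baseline protects a comparison when it is fixed before anyone has a reason to move it. Here the sessions that would naturally serve as the on-task baseline also set a payment threshold, and the payment exists in one arm only. A participant who knows the arm and the rule has a small reason to work less in sessions 1-2. A staff member who knows the arm could, without intending to, run those sessions differently.

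Any such effect would lower the starting point in the VR + contingency arm and leave the other two alone. In an analysis of change, a lowered start looks the same as a gain. The most direct exposure is the set of Phase 3 effect sizes for objective attention. The timetable in section 1.10 places these just before the Go/No-Go evaluation, though the documents do not say whether on-task change is a criterion for it.

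**Working it through.** **1. Does allocation come before sessions 1-2?** Three places point that way: randomisation follows the initial evaluation; the two sessions are part of the 12-session course and appear inside each arm's description; and section 1.3 C gives them their own week after the initial evaluation. No sentence says it outright. Being randomised and then scheduled for the headset does not strictly exclude non-VR sessions held before randomisation.

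**2. The bonus as stated.** 2 x $10 = $20, and $110 + $20 = $130, which matches section 4.6 B.

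**3. What a low baseline does to the target.** Let the recorded baseline be (1 - s) times the true one, and let g be the true proportional gain. The rule is met when (1 + g)/(1 - s) >= 1.25, that is, when g >= 1.25(1 - s) - 1.

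| Baseline understated by s | True gain needed |
|---|---|
| 0% | 1.25 x 1.00 - 1 = 25% |
| 5% | 1.25 x 0.95 - 1 = 18.75% |
| 10% | 1.25 x 0.90 - 1 = 12.5% |
| 20% | 1.25 x 0.80 - 1 = 0% |

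Conversely, with no true gain the baseline must be 1/1.25 = 0.80 of its true value (20% low). With a true gain of 10% it must be 1.10/1.25 = 0.88 (12% low). These figures describe the rule, not anyone's expected behaviour.

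**4. Is there another pre-intervention value?** For ratings of concentration, homework motivation and homework effort there is: section 1.3 A takes them at the initial evaluation. For keystroke and mouse data there is not, so sessions 1-2 are the only possible pre-intervention value, if the data are captured there at all. Sections 1.3 B (10 sessions) and 1.6 B (inside VR), read literally, suggest they are not. Section 4.6 B requires a focus value from those sessions. The three passages do not agree.

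**5. Which analyses are exposed?**
- Phase 3 time-by-intervention effect sizes and trajectories for objective attention: exposed if sessions 1-2 are the reference. Section 6.1 does not define the time factor.
- Phase 4 mixed model: most naturally read as using the ratings of functioning that section 1.3 collects at baseline, outcome and follow-up. It is not exposed unless on-task data are analysed as change from sessions 1-2.
- Phase 4 mediation: exposed only if on-task data serve as a mediator with sessions 1-2 as pretest. Section 1.3 (Phase 3) counts algorithm data among the mechanisms; section 1.1 B names only concentration, effort and motivation.
- Ratings referenced to the initial evaluation: not exposed.
- Levels in sessions 3-12 compared between randomised arms: not exposed, because a low baseline does not alter them.

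**6. Size.** The documents give no data from which to estimate how many people would lower their baseline, or by how much. I put no figure on the bias in the effect estimate.

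**The case against.** The case against has several parts, and most of them limit the point.

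- *The order is inferred.* True. If the sponsor already allocates after session 2, one sentence settles the matter.
- *The mechanism needs knowledge of the arm and the rule during sessions 1-2.* True. The consent pages are not available to us, so the timing of disclosure cannot be checked, and its absence is not counted as a fault. A reader might infer from the N/A against deception and concealment in section 4.4 B that the arm is disclosed at once. That entry concerns deceiving participants during consent, not allocation, and does not support the inference.
- *Focus may not mean on-task behaviour.* Possible. Reading comprehension is also done each session, and it has an initial-evaluation value. This is why the term needs defining.
- *The incentive is weak.* It is $20 at most, participants are doing their own homework, and section 4.7 A has staff supervising each session closely. All of this lowers the likelihood; none of it removes the asymmetry.
- *The analysis could detect or avoid the problem.* Partly right. Levels in sessions 3-12 are unaffected. A lowered baseline would also appear as imbalance between arms. With 15 per arm, though, the standard error of a standardised difference near zero is sqrt(2/15) = 0.37, so Phase 3 could show only a gross shift. With 84 per arm it is sqrt(2/84) = 0.15, so Phase 4 could show a large one.

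What stands is a one-sided incentive on the only possible pre-intervention value of a Phase 3 primary variable, with no stated safeguard and a nearly free remedy.

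**Conclusion.** The point holds as a design weakness that should be fixed, with medium confidence. It is a risk of unknown size, possibly zero, and not a demonstrated bias. It rests on three readings that the sponsor can confirm or correct: allocation precedes sessions 1-2; focus in the bonus rule is, or is closely tied to, the on-task measure; and that measure is recorded in the non-VR sessions.

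Two stronger conclusions might be inferred, and neither is supported. One is that the main Phase 4 results are compromised: its model is most naturally read as using ratings whose baseline is the initial evaluation, and on-task exposure there is conditional. The other is that no later analysis could recover from a lowered baseline: a change analysis could not, but a randomised comparison of levels in sessions 3-12 does not depend on that baseline.

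**What to change.** 1. In Phases 3 and 4, keep the allocation from participants and session staff until sessions 1-2 are complete and their data stored, and say so in section 1.3 A. The bonus can stay, because until the arm is known the incentive is the same for everyone. This adds no visits, leaves 45 and 252 unchanged, and alters only the date on which the arm is disclosed.
2. Alternatively, randomise after session 2. Allocation then moves by about one week, and anyone who stops during sessions 1-2 is not randomised and may need replacing.
3. In section 6.1, name the reference baseline for on-task behaviour. Add a sensitivity analysis that compares on-task levels in sessions 3-12 between arms without the sessions 1-2 reference. The cost is a few lines of text and, for that analysis, the precision that a baseline adjustment might have given.
4. Define focus in section 4.6 B, and reconcile that section with sections 1.3 B and 1.6 B on whether keystroke and mouse data are captured in the two non-VR sessions.
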